9.7.3 Stopping the Trial Based on Interim Safety Data

In case of concern for safety issue arises from DSMB, the trial may be stopped temporarily or permanently if the serious adverse event rate (SAEs related to the study treatment) exceeds a clinically acceptable rate of 10% in either arm. Data for events will not be evaluated until the first 30 subjects have completed 30 day post treatment follow-up for each arm.

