3. STUDY DESIGN

Multi-center, prospective, randomized, open-label, pilot study

ARM 1: LDV/SOF x 12 weeks

ARM 2: LDV/SOF + RBV x 12 weeks

Number subjects:

Multi-center

50 subjects, with 25 subjects in each arm

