6.2.2 Intervention and Evaluations

Once the subject has been successfully randomized, the intervention should be initiated upon that day, but must be initiated within 5 days in case of extenuating circumstances.

Study evaluations must take place within the time window indicated on the Schedule of Evaluations (Section 6.1).

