9.3 Sample Size Estimation for the Primary Outcome

For a definitive trial, if we assume an efficacy rate of 95% with an acceptable noninferiority margin of 10%, 75 subjects would be needed in each arm to provide an alpha level of 0.05 with 80% power to demonstrate noninferiority. Assuming a 10% dropout rate (indicating randomization, but failure to receive a dose of study medication), 85 subjects would need to be randomized in each arm. In this pilot study of 50 subjects, we will be able to obtain estimates of these rates for the two groups for use in the future definitive trial.

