9.7 Safety Analysis

9.7.1 Safety Outcomes

Safety outcomes include the proportion of subjects who experience any treatment-related serious adverse events (SAEs) during the treatment phase and up to 30 days following completion of the treatment.

Overall safety and tolerability of each regimen will be estimated by measuring the incidence of:

- Development of medication intolerance requiring dose reduction, temporary withdrawal, or removal of the study drug(s)
- Incidence of the need for supportive medications (erythropoietins, colony-stimulating factors)
- Incidence of intolerance requiring dose reduction, temporary withdrawal, or removal of immunosuppressants
- Overall and opportunistic infections
- Biopsy-proven rejection rates
- Mortality
- Graft loss

Other specific SAEs to be monitored may be added in consultation with the DSMB. The cumulative incidences of each outcome will be estimated along with 95% confidence intervals.

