9.7.2 Interim Safety Monitoring

The Data Safety Monitoring Board (DSMB) will review study safety event rates, center performance, adverse events (AEs), and serious adverse events (SAEs) periodically. This review will identify any clinical, operational, or other data issues that might require changes or adjustments in the way in which the trial is conducted as well as any safety issues that may need to be addressed. In order to accommodate this, the Data Coordination Unit (DCU) will generate safety monitoring reports as well as a comprehensive statistical report periodically for the DSMB. These reports will contain compiled data on enrollment, demographic and baseline characteristics, eligibility and protocol violations, safety data, concomitant medications and procedures, and data quality (e.g., timeliness of data entry, and number of data clarification requests generated and resolved). All AEs and SAEs will be coded using MedDRA and summarized in terms of frequency of the event, number of subjects having the event, timing relative to randomization, and severity and relatedness to treatment. For each review, the DCU will generate two statistical reports – an open, blinded report to be distributed to the Executive Committee and the DSMB, and a closed report to be distributed only to the DSMB. For the closed report only, the statistics will also be provided by partially blinded treatment group (A vs B). If the DSMB wishes to be completely unblinded for closed reports, a sealed treatment identification envelope will be provided to the DSMB; this envelope can be opened at the discretion of the DSMB. The closed report will also contain data listings identifying subjects with specific safety outcomes such as mortality.

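### The 10% related-SAE stopping criterion waits for 30 subjects in each arm, but the trial plans only 25 per arm, so as written it can never be evaluated

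*Combined protocol and SAP*

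**What the plan says.** Section 9.7.3 holds the protocol's only numerical safety stopping criterion. If the DSMB has a safety concern, "the trial may be stopped temporarily or permanently" when the rate of treatment-related SAEs "exceeds a clinically acceptable rate of 10% in either arm". The next sentence sets a precondition: "Data for events will not be evaluated until the first 30 subjects have completed 30 day post treatment follow-up for each arm".

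The planned size is stated twice. Section 3 gives "50 subjects, with 25 subjects in each arm", and Section 9.3 repeats the total ("In this pilot study of 50 subjects"). The larger figures in Section 9.3, 75 and 85 per arm, belong to a future definitive trial.

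Two other sections bear on the rule. Section 9.7.1 counts treatment-related SAEs "during the treatment phase and up to 30 days following completion of the treatment", the same 30-day window used in 9.7.3. Section 9.7.2 says the DSMB "will review study safety event rates, center performance, adverse events (AEs), and serious adverse events (SAEs) periodically" and names no minimum number of subjects.

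**The concern.** The precondition in 9.7.3 asks for more subjects per arm than Section 3 will enrol. Read plainly, the protocol names the related-SAE rate it regards as tolerable and then forbids comparing the data with it at any point in the trial.

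A second ambiguity adds to this. The sentence does not say whether the events it holds back are only those used for the 10% criterion or all event data. The wider meaning would conflict with the periodic review in 9.7.2. A DSMB following the text could conclude that it may not apply the 10% limit at all, or could be unsure what it may look at and when.

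What is at stake is the numerical trigger, not safety oversight as a whole.

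**Working it through.** **Inputs.** 50 subjects, 25 per arm (Sections 3 and 9.3); minimum of 30 with 30-day post-treatment follow-up for each arm, and a limit of more than 10% in either arm (9.7.3); 12 weeks of treatment in both arms (5.1); treatment normally starts on the day of randomisation but "must be initiated within 5 days in case of extenuating circumstances" (6.2.2).

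**Plain reading: 30 in each arm.**
- Planned per arm: 50 / 2 = 25.
- Required in total: 2 × 30 = 60.
- Shortfall: 30 − 25 = 5 per arm, or 60 − 50 = 10 in total.
- With 50 subjects the smaller arm can never exceed 25, so no imbalance in allocation rescues the condition.

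**Alternative reading: 30 in total.**
- 30 / 50 = 60% of the sample, about 15 per arm if balanced.
- Follow-up needed: 84 + 30 = day 114 after first dose, or up to 114 + 5 = day 119 after randomisation.
- If the 30th subject starts at time T, the look falls at T + 114. A subject who started at time t is still on treatment then only if t + 84 > T + 114, that is, t > T + 30. Subjects not yet started would also benefit; at most 50 − 30 = 20 subjects fall in these two groups together. This assumes a full, uninterrupted course. The documents give no accrual rate, so the actual number cannot be derived.

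**What a reachable look would do.** For n subjects in an arm, let k be the smallest count giving a rate above 10%. Then P(X ≥ k) = 1 − Σ C(n, j) p^j (1 − p)^(n − j), summed over j = 0 to k − 1. Example, n = 15, k = 2, p = 0.05: 1 − 0.95^15 − 15 × 0.05 × 0.95^14 = 1 − 0.4633 − 0.3658 = 0.171. The true rates p and the looks at 10, 15 and 20 are illustrative assumptions.

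| Single look, one arm | p = 5% | 10% | 20% | 30% |
|---|---|---|---|---|
| ≥2 of 10 | 8.6% | 26.4% | 62.4% | 85.1% |
| ≥2 of 15 | 17.1% | 45.1% | 83.3% | 96.5% |
| ≥3 of 20 | 7.5% | 32.3% | 79.4% | 96.5% |

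The rule applies to either arm. With independent arms at the same true rate, the probability that at least one crosses is 1 − (1 − P)². Repeated looks were computed by exact recursion.

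| Either arm crosses | p = 5% | p = 10% |
|---|---|---|
| One look at 10 per arm | 16.5% | 45.8% |
| One look at 15 per arm | 31.3% | 69.9% |
| One look at 20 per arm | 14.5% | 54.2% |
| Looks at 10, 15 and 20 per arm | 32.7% | 73.0% |
| After every subject, 1 to 25 per arm | 67.7% | 92.9% |

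Some minimum denominator is needed: one event among 9 subjects is 1/9 = 11.1%, already above the limit, whereas 1/10 is not.

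**The case against.** The strongest reply is that little protection is lost. The 9.7.3 rule is permissive and starts from a DSMB concern; it is not an automatic boundary. Under 9.7.2 the DSMB receives safety reports by arm, with SAEs summarised by relatedness, and may unblind fully. Section 10.4 has the medical safety monitor review each reported SAE and provides a route to the DSMB when event rates look unexpectedly high. Section 11.2 allows the IRB, sponsor or regulators to discontinue the study at any time. The withholding and discontinuation criteria for individual subjects in Sections 5.1, 7 and 8 apply from the start. The 10% figure also stays on the page as a reference.

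All of that stands, and it limits the consequence. It does not make the precondition attainable, and 9.7.2 does not say that it overrides 9.7.3.

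The sentence might also mean 30 subjects overall, with results then examined by arm. That is possible but less natural: the 30 is tied to each arm, and the preceding sentence sets its limit by arm. A safety rule that is either impossible to evaluate or evaluable at about 15 per arm still needs correcting. How late the second version would come depends on accrual, which the documents do not give.

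Finally, the either-arm figures assume equal rates although only Arm 2 receives ribavirin, and a true rate of 10% sits on the limit itself. They are a guide to scale. The contradiction does not depend on them.

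**Conclusion.** The concern holds. On its plain reading, Section 9.7.3 sets a condition that is 5 subjects per arm beyond the size fixed in Section 3, so the only numerical safety stopping criterion cannot be evaluated in this trial. This is an internal contradiction in the current text, and it rests on no assumption beyond taking the words for each arm at face value.

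If 30 in total was intended, the criterion is usable after 60% of the sample has completed follow-up, and the wording is at fault. Either way the text must be corrected before the DSMB relies on it. The finding is limited to the numerical trigger; the remaining oversight is intact unless the sentence is given its wider meaning.

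**What to change.** Amend Section 9.7.3 so that it agrees with Sections 3 and 9.7.2:

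1. State whether the 30 was meant per arm or in total, and replace it with an evaluation point that can be reached within 25 per arm while other subjects are still to be treated or on treatment.
2. State that the sentence limits only the 10% criterion and does not restrict the DSMB's periodic review.
3. Keep a minimum denominator, so that a single early event does not cross the limit.
4. State the number of looks and the exact probabilities of crossing for the either-arm rule.

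The sponsor and DSMB should choose the count and the number of looks; those tabulated above are illustrations, not proposals.

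The cost is a one-paragraph amendment, with no added subjects or procedures. The downside is a real chance of crossing without a true excess. For a single look at 10 to 20 per arm, either arm crosses with probability 14.5% to 31.3% at a true 5%, and 45.8% to 69.9% at a true 10%; more looks raise this. Because crossing permits a pause and does not compel one, the DSMB can weigh that risk case by case.

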10. DATA COLLECTION, SITE MONITORING, ADVERSE EVENT REPORTING

10.1 Data Processing

Data management will be handled by DCU. All study activities will be conducted in coordination with the study PI, and will use an electronic data acquisition method where all clinical data on enrolled subjects will be entered by the site personnel in real time. The latest version of each CRF will be available as a PDF file on the study website for

use as worksheets and source documents by study personnel. The study data will be managed (including data queries) by DCU using the WebDCU™ system. This user-friendly web-based database system, developed by DCU, will be used for regulatory document management, subject randomization, data entry, data validation, project progress monitoring, subject tracking, user customizable report generation and secure data transfer.

10.2 Data Security and Confidentiality

During the course of the trial, user access to the files with subject identifiers, treatment assignment and files with study outcomes will be restricted to core staff. In addition to use of passwords and other security measures, all documents containing identifying information on individuals or physicians are considered confidential materials and will be safeguarded to the greatest possible extent. No information, which identifies a specific person, hospital, or physician, will be released to, or discussed with anyone other than study team members.

Because the DCU uses a web-based system, source documents and CRFs will remain at the participating sites. The study database only identifies study subjects by unique study identification codes. All data will be stored in a manner that is HIPAA compliant, without the ability to track the information back to a specific subject except through a password protected system. All collected information about a subject will be stored by a unique identification code. All DCU personnel have current Human Subjects Protection Training Certification. Clinical information will not be released without written permission of the subject, except as necessary for monitoring by IRB, the FDA, OHRP, the sponsor, or the sponsor's designee.

10.3 Data Quality Assurance

The study data will be managed (including data queries) by DCU using the WebDCU™ system. This user-friendly web-based database system, developed and validated by the DCU, will be used for regulatory document management, subject randomization, data entry, data validation, project progress monitoring, subject tracking, user customizable report generation and secure data transfer. In addition to the study database, the DCU will provide the clinical site staff access (via password) to a standard set of web-enabled tools, including subject visit calendar, subject accrual status, case report form completion status, and outstanding data clarification request status pertaining to their respective clinical sites. Furthermore, all approved study materials, such as the protocol, informed consent template and manual of procedures, will be housed on the website to ensure that the clinical sites always have access to the most current trial documents.

Data should be independently entered by the designated personnel at each clinical site into WebDCU™ within the time intervals specified in the schedule of assessments. Enrollment data, however, must be entered into the WebDCU™ database before the subject can be randomized. Serious adverse events must be entered into the WebDCU™ within 24 hours of the site staff's first awareness of the event. It is critically important to the effective and efficient conduct of the study that data be entered in a timely manner. An electronic copy of the CRFs will be made available to the clinical sites prior to initiation of the study to be used as worksheets to capture the required data for the study. The DCU staff will perform range verification, consistency checks, and quality assurance on the data. The staff at the DCU will contact the sites regarding missing data or queries on CRF data. They will maintain direct contact with the staff at the participating sites to ensure the study is conducted according to the Good Clinical Practice Guidelines and all applicable regulations.

Experienced clinical research monitors will be contracted through the DCU to perform on site source data verification (SDV) of key outcome and safety data variables during the study. In addition to data verification, the monitor will evaluate drug accountability and site facilities. The CRFs and corresponding source documents should be made available to the study monitor at each site visit. It is also expected that the PI, or a designated member of the research staff, will be available during the monitoring visit to review the data and resolve any queries.

10.4 Adverse Experience Reporting

In order to ensure prompt reporting of adverse events, all adverse events (as well as all related study data) must be entered into the WebDCU™ within five days of collection date. All serious adverse events (SAEs) must be reported on the WebDCU™ within 24 hours of the study site staff first being made aware of its occurrence. The site investigators are required to provide relevant information, including description of the adverse event, date/time of onset and resolution, severity and seriousness, action taken, and suspected relationship to the study treatment.

Reporting of any serious adverse event will trigger notification of the event to the DCU Project Manager (PM) and the independent Medical Safety Monitor (MSM). The MSM will conduct an independent review of each of these events to determine if it is serious, unexpected, and study treatment related.

Periodically throughout the study, the MSM will review reports on the incidence rates of all reported adverse events, whether serious or not. Should such monitoring uncover issues that may threaten subject safety (e.g. unexpectedly high rate of adverse events), the study statistician and principal investigator will prepare a report to be submitted to the DSMB for their review and further actions to be taken, if any.

11. HUMAN SUBJECTS

11.1 Institutional Review Board (IRB) Review and Informed Consent

This protocol, the ICF, and any subsequent modifications must be reviewed and approved by the local IRB at each of the participating institutions. A signed and dated ICF must be obtained from the subject as defined in 21CFR50.3. The ICF must also be signed and dated by a member of the study staff qualified to be delegated the authority to obtain informed consent, and a witness (if required by the local IRB). A copy of the ICF must be given to the subject and the consent process must be documented in the subject's medical record. The PI or delegated sub-Investigator is responsible for ensuring that informed consent is obtained from each patient prior to conducting any study-related activities.

No deviations from or changes to the study protocol should be initiated except when necessary to eliminate immediate hazard to the subject. However, the IRB, DCU, and Study Sponsor must be informed of this as soon as possible thereafter. It is the study site PI's responsibility to report SAEs occurring during the study to their IRB, as required and as soon as possible.

11.2 Study Modification/Discontinuation

The study may be modified or discontinued at any time by the IRB, the sponsor, the OHRP, the FDA, or other government agencies as part of their duties to ensure that research subjects are protected.

12. PUBLICATION OF RESEARCH FINDINGS

Publication of the results of this trial will be reviewed and approved by all coinvestigators. Final results will be submitted to ClinicalTrials.gov. Any presentation, abstract, or manuscript will be made available for review by the sponsor prior to submission.

APPENDIX I

US Public Health Service (PHS) Guideline for Reducing Human Immunodeficiency Virus, Hepatitis B Virus, and Hepatitis C Virus Transmission Through Organ Transplantation, 2013 ed.

Donor at Increased Risk for recent HIV, HBV, and HCV infection

1. People who have had sex with a person known or suspected to have HIV, HBV, or HCV infection in the preceding 12 months
2. Men who have had sex with men (MSM) in the preceding 12 months
3. Women who have had sex with a man with a history of MSM behavior in the preceding 12 months
4. People who have had sex in exchange for money or drugs in the preceding 12 months
5. People who have had sex with a person who had sex in exchange for money or drugs in the preceding 12 months
6. A child who is ≤ 18 months of age and born to a mother known to be infected with, or at increased risk for, HIV, HBV, or HCV infection
7. A child who has been breastfed within the preceding 12 months and the mother is known to be infected with, or at increased risk for, HIV infection
8. People who have injected drugs by intravenous, intramuscular, or subcutaneous route for non-medical reasons in the preceding 12 months
9. People who have been in lockup, jail, prison, or a juvenile correctional facility for more than 72 consecutive hours in the preceding 12 months
10. People who have been newly diagnosed with, or have been treated for, syphilis, gonorrhea, *Chlamydia*, or genital ulcers in the preceding 12 months
11. Donor who is at increased risk for recent HCV infection only:
 - a. People who have been on hemodialysis in the preceding 12 months

APPENDIX II
Milan Criteria

1. A single HCC nodule with a maximum size of 5 cm
OR
2. Up to 3 HCC nodules with the largest not exceeding 3 cm
AND
No macrovascular invasion
